### 6.4. Safety Population [SAF]

The safety population (SAF) will contain all patients who received at least one dose of randomized study medication (i.e., patients who received at least one dose of Humira in Group I or Hulio in Group II of the Randomized Interchangeable Treatment Period).

## 6.5.Per Protocol Population [PPP]

The Per Protocol Population (PPP) will contain all randomized patients in the Safety population who have assessments prior to randomization and at least once post-randomization for at least one secondary efficacy endpoint and who do not have any important protocol violations impacting efficacy.

Reasons for exclusion can be, but not limited to:

Non-compliance with the inclusion or exclusion criteria.

Insufficient essential efficacy data for the secondary analysis.

Intake of prohibited medication.

Non-compliance with randomization criteria.

Non-compliance with the study treatment.

## 6.6. Pharmacokinetic Population (PKP)

The Pharmacokinetic Population (PKP) will contain all patients, who provide at least one primary PK parameter from the intense PK sample intervals in both run-in phase and randomization phase without major protocol violation relevant for primary endpoint evaluation.

Relevant major protocol deviation critical for primary endpoint evaluation may include:

Incorrect trial medication taken, i.e., the patient received at least one dose of trial medication the patient was not assigned to during the study until including Visit 14 (Week 26) dosing.

Incorrect or incomplete dose of trial medication taken; the incomplete dose will be treated as missed dose.

Document: \\ieedc-vnasc01\Biosdata\\Viatris\HULIO\HAB34991\Biostatistics\Documentation\SAP

Author: Version Number: 2.0

Version Date: 29Nov2023

Template No.: CS\_TP\_BS016 Revision 7 Reference: CS\_WI\_BS005

Effective Date: 01Nov2021

Page 19 of 48

Use of restricted medications with suspected impact on PK

Dosing day deviation of trial medication.

An early or delay of dosing by 7 or more days (resulting in a dosing interval length of less than 7 days or more than 21 days) will be considered as a missed dose.

Missed doses during run-in phase (until including Visit 6).

If only one dose until including Visit 4 (Week 6) was missed, the subject can be included in the statistical analysis population. If more than one dose was missed until including Visit 6 (Week 10), the subject will be excluded from statistical analysis population. If dose at Visit 5 or 6 was missed, the subject will be excluded from statistical analysis population.

Missed doses during randomized phase (from Visit 7 until Visit 14).

If only one dose from Visit 7 (Week 12) until Visit 12 (Week 22) was missed, the subject can be included in the statistical analysis population. If more than one dose was missed until including Visit 14 (Week 26), the subject will be excluded from statistical analysis. If dose at Visit 13 or 14 was missed, the subject will be excluded from statistical analysis population.

Missed doses after randomized phase including Visit 15 (Week 28).

If doses are missed from Visit 15 (Week 28) until end of the study, the subject will not be excluded in statistical analysis population.

Blood draw deviations from planned PK sampling times.

PK sampling windows in the protocol were defined for operative reasons. Deviations will not necessarily lead to exclusion from analysis of PK endpoints. In the intensive PK interval in run-in phase, any PK sample deviation is more than half of the interval between the two samples, the PK sample will be treated as missing for the scheduled time point and it will be considered as the sample at the other time point. In the intensive PK interval in the randomization phase, except the Predose of Visit 15 (Week 28) any PK sample deviation of more than 24 hours, the PK sample will be treated as missing for the scheduled time point and it will be considered as the sample at the other time point. For Visit 15 (Week 28), samples will be treated as missing if the deviation is more than 168 hours (7 days).

Missing PK samples.

If missing two or more plasma samples during the intense PK sample interval from Visit 6 (week 10) to Visit 7 (Week 12), the subject will be excluded from the statistical analysis population.

Document: \\ieedc-vnasc01\Biosdata\Viatris\HULIO\HAB34991\Biostatistics\Documentation\SAP

Author: Version Number: 2.0

Version Date: 29Nov2023

Template No.: CS\_TP\_BS016 Revision 7 Reference: CS\_WI\_BS005

Page 20 of 48

If missing three or more plasma samples during the intense PK sample interval from Visit 14 (Week 26) to Visit 15 (Week 28), the subject will be excluded from the statistical analysis population.

For analyses and displays based on PKS, subjects will be classified according to treatment received.

### 7. GENERAL CONSIDERATIONS

### 7.1. Reference Start Date and Study Day

All summaries by period defined in the SAP refers to the analysis period. The analysis period consists of screening, Run-in Period, and Randomized Interchangeable Treatment Period (study diagram). Each period is defined as below:

Screening period is defined as study period from informed consent date prior to administration of Humira at Week 1.

Run-in Period is defined as study period on or after administration of Humira at Week 1 and before randomization at Week 12, or until last study participation date if patients withdrew/discontinued before Week 12.

Randomized Interchangeable Treatment Period is defined as study period from the randomization at Week 12 until Week 28 or until last study participation date if patients withdrew/discontinued. While presenting the data Week 28 (EOT) assessment will also be included.

Overall period is defined as study period consisting of above 3 periods and including follow up (Week 30/EOS). Study Day will be calculated from the reference start date and will be used to show start/stop day of assessments and events. It will appear in every listing where an assessment date or event date appears.

Reference start date is defined as the day of the first dose of study medication, i.e., Humira in the Run-in Period (Week 1/Visit 1) (Day 1 is the day of the first dose of study medication).

- If the date of the event is on or after the reference date, then:
- Study Day = (date of event reference date) + 1.
- If the date of the event is prior to the reference date, then:
- Study Day = (date of event reference date).

In the situation where the event date is partial or missing, Study Day, and any corresponding durations will appear

Document: \\ieedc-vnasc01\Biosdata\Viatris\HULIO\HAB34991\Biostatistics\Documentation\SAP

Author: Version Number: 2.0

Version Date: 29Nov2023

Template No.: CS\_TP\_BS016 Revision 7 Reference: CS\_WI\_BS005

Page 21 of 48

partial or missing in the listings.

#### 7.2.Baseline

Unless otherwise specified, baseline is defined as the last non-missing measurement taken prior to reference start date (including unscheduled assessments). i.e., Baseline is the last non-missing measurement taken prior to the first dose of Humira in the Run-in Period (Week 1/ Visit 1). In the case where the last non-missing measurement and the reference start date coincide, that measurement will be considered pre-baseline if the assessment is planned per protocol to take place prior to first study medication administration. For Hematology, Clinical chemistry, Urinalysis, Vital signs (HR, RR, BP, temperature) and 12-Lead ECG assessments, baseline value for Randomized Interchangeable Treatment Period will be the last non-missing measurement collected prior to the first medication dose taken in Randomized Interchangeable Treatment Period (i.e., Week 12/Visit 7).

### 7.3. Retests, Unscheduled Visits and Early Termination Data

In general, for by-visit summaries, data recorded at the nominal visit will be presented. Unscheduled measurements will not be included in by-visit summaries.

In the case of a retest (same visit number assigned), the latest available measurement for that visit will be used for byvisit summaries.

Early termination data will be mapped to the ET/End of Study Follow-Up visit for by-visit summaries.

Listings will include scheduled, unscheduled, retest and early discontinuation data.

## 7.4. Windowing Conventions

Window convention is not applicable for this study.

For subjects who are randomized, have Week 12/ Visit 7 assessments for efficacy parameters (PASI and sPGA) and terminated from the study early, their PASI and sPGA assessments performed at the early termination visit will be remapped to the nearest protocol defined scheduled Visit for PASI and sPGA assessments (target day ±3 days). If an assessment cannot be remapped to a scheduled visit, the assessment will be considered as unscheduled and hence will not be considered for efficacy analysis. This remapping is done since in the EDC there is no separate early termination visit and for subjects who terminated early, their assessments performed at early terminations visits are captured at Week 28/ Visit 15 even though they are not actual Week 28/ Visit 15 assessments.

Document: \\ieedc-vnasc01\Biosdata\Viatris\HULIO\HAB34991\Biostatistics\Documentation\SAP

Author: Version Number: 2.0

Version Date: 29Nov2023

Template No.: CS\_TP\_BS016 Revision 7 Reference: CS\_WI\_BS005

Page 22 of 48

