## 19.5. Immunogenicity Analysis

The assay includes three tiers of analysis designated as screening, confirmation, and titration, respectively. Samples identified as positive in the screening assay will be tested in a confirmatory assay that employs a 0.1% false positive rate. Confirmed positive samples will be further evaluated for ADA titer. Neutralizing capacity (Nab) of the antibodies will be evaluated for samples in which anti-drug antibodies have been confirmed to be present.

Immunogenicity data, including subject ID, visit, anti-drug antibody (ADA) results, ADA titers, and neutralizing antibody results (Nab) will be presented.

Immunogenicity to adalimumab will be descriptively summarized by treatment group at Week 28 time point and include:

- Incidence of positive ADA and NAb response
- Titer of subjects with positive ADA response
- Change from Week 12 in ADA and NAb incidence, and ADA titer

Document: \\ieedc-vnasc01\Biosdata\Viatris\HULIO\HAB34991\Biostatistics\Documentation\SAP

Author: Version Number: 2.0

Version Date: 29Nov2023

Template No.: CS\_TP\_BS016 Revision 7 Reference: CS\_WI\_BS005

Page 37 of 48

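### SAP 7.3 and 7.4 conflict on early-termination data, so the Week 28 ADA, NAb, titre, laboratory and vital-sign summaries may include samples taken earlier

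*SAP*

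**What the plan says.** **Storage.** SAP 7.4 states that "in the EDC there is no separate early termination visit" and that, for patients who left early, "their assessments performed at early terminations visits are captured at Week 28/ Visit 15". It describes these assessments as "captured at Week 28/ Visit 15 even though they are not actual Week 28/ Visit 15 assessments". The plan thus acknowledges that the stored visit label is wrong for these records.

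**Correction for efficacy.** For randomised patients with Week 12 efficacy data who leave early, "their PASI and sPGA assessments performed at the early termination visit will be remapped to the nearest protocol defined scheduled Visit", within 3 days of the target day. Anything that fits no visit counts as unscheduled and drops out of the efficacy analysis. No other date check is given in that section, which opens with "Window convention is not applicable for this study".

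**General rule.** SAP 7.3 says that "for by-visit summaries, data recorded at the nominal visit will be presented", and also that "Early termination data will be mapped to the ET/End of Study Follow-Up visit for by-visit summaries".

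**Available visits.** The output visit list in SAP Appendix 1 ends with Week 28 (Visit 15) and Week 30 (Visit 16). No row is labelled early termination. SAP 7.1 equates follow-up with Week 30/EOS.

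**Affected summaries.** ADA and NAb incidence and ADA titre at Week 28 are secondary endpoints (Protocol synopsis; SAP 2.2.2). SAP 19.5 has them "descriptively summarized by treatment group at Week 28 time point", with change from Week 12, and gives no date rule. SAP 19.3 and 19.6 call for laboratory and vital-sign tables by visit.

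**The concern.** The reason given for remapping PASI and sPGA is how the EDC stores visits. That reason applies equally to blood samples and vital signs taken at the same early visit, but for these the plan gives no step that can be carried out as written. Two programmers could both follow the SAP and produce different Week 28 tables.

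The Week 28 immunogenicity readout matters here because it is meant to describe patients after the full switching sequence, and SAP 20.2.7 itself says that ADA lowers exposure. The Safety population (SAP 6.4) keeps anyone with one randomised dose, so early leavers are in it. If their samples carry a Week 28 label, the reported incidence mixes different exposure times, and in the switching arm different numbers of switches. If exits differ by arm, the mix differs by arm.

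**Working it through.** The plan gives no figure on this point. The check sets the rules side by side and then sizes the effect under stated assumptions.

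**1. Scale figures (SAP 4).** 280 evaluable patients and a 15% non-evaluable rate give 280 / (1 − 0.15) = 329.4, which rounds to the stated 330 randomised; 330 / 2 = 165 per arm.

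**2. How early a mislabelled sample could be.** Randomisation is at Week 12 and the label says Week 28: 28 − 12 = 16 weeks at most, slightly less for a sample taken after the Week 12 dose.

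**3. How many switches would have occurred.** By Appendix 1 the switches in Group 2 start at Weeks 12, 16 and 20. A Group 2 patient in the Safety population who leaves before Week 16 has had one switch, and one who leaves between Weeks 16 and 20 has had two. Only exits from Week 20 on follow the third.

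**4. Where a non-efficacy early-termination record would go.**

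| Rule followed | Result |
|---|---|
| 7.3, nominal visit | Week 28 row, because the record is stored as Visit 15 |
| 7.3, early-termination/follow-up visit, using Appendix 1 rows | Week 30 row, pooled with follow-up |
| 7.3, early-termination/follow-up visit, adding a row | Correctly separated, but no such row or method is specified |
| 7.4, by analogy | Nearest scheduled visit or unscheduled, but 7.4 limits this to PASI and sPGA |

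The first two mislabel the record, in different ways. The SAP does not choose among the four.

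**5. What is already protected.** PK analyses and concentration summaries use the PK population (SAP 20). SAP 6.6 excludes anyone who missed the Visit 13 or 14 dose, which removes patients who stopped before Week 26. It also treats a Visit 15 PK sample more than 168 hours off as missing. SAP 20.1 adds a 506-hour limit after the preceding dose and brings the concentration to 336 hours for AUC when the deviation exceeds 12 hours.

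**6. Size of the shift.** Let f be the share of Week 28 values that are really early-termination samples, pE the ADA incidence in those samples, and pC the incidence in true Week 28 samples. Reported incidence is (1 − f) × pC + f × pE, so the shift is f × (pE − pC). Neither f nor the gap is in the documents; both are assumed. The 15% ceiling for f borrows the non-evaluable rate.

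| f | f × 330 | Shift, 10-point gap | Shift, 30-point gap |
|---|---|---|---|
| 3% | 9.9 | 0.3 | 0.9 |
| 5% | 16.5 | 0.5 | 1.5 |
| 10% | 33 | 1.0 | 3.0 |
| 15% | 49.5 | 1.5 | 4.5 |

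Shifts are in percentage points and can go either way. With the same gap in both arms but unequal exits, the between-arm distortion is the difference in f times the gap. For 5% against 10% it is 0.05 × 10 = 0.5 to 0.05 × 30 = 1.5 points; for 5% against 15% it is 0.10 × 10 = 1.0 to 0.10 × 30 = 3.0 points.

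**The case against.** The strongest reply is that SAP 7.3 already holds a general rule, not limited to any type of assessment, and that 7.4 is simply the efficacy exception to it. Mapping is done in the analysis datasets and does not need an EDC visit; 7.4 itself shows that such records can be found and moved. On that reading nothing is mislabelled.

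Part of this stands. A reader might infer from 7.4 alone that PASI and sPGA are the only data remapped, or that the Week 28 tables will certainly contain early samples. The documents do not support either statement, because 7.3 does intend to move the rest. But 7.3 names a destination without defining it, the only follow-up row in Appendix 1 is Week 30, and its nominal-visit sentence points back to Week 28. The intention is there; the instruction is not.

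Other limits also stand:

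- A reader might extend the point to the Week 28 trough. SAP 6.6, 20 and 20.1 already exclude or time-limit those samples.
- A reader might suppose that Group 2 patients with no switch could be counted. The Safety population requires a Hulio dose in Group 2, so each has had at least one.
- The 15% in SAP 4 is a PK non-evaluable rate. It also covers dosing deviations, restricted medication and missing samples, and not every leaver need give a sample. It is a ceiling, not an exit rate.
- The immunogenicity sampling visits are blanked in the protocol synopsis, and the schedule of events and output templates are not in the supplied text. Whether ADA is drawn at early termination cannot be confirmed.
- The affected summaries are descriptive, and SAP 19 plans no between-group comparison of safety data unless a section says otherwise.

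**Conclusion.** The point holds as a conflict between SAP 7.3 and 7.4 that leaves non-PK, non-efficacy early-termination records without a workable visit assignment. The Week 28 ADA, NAb and titre results, their change from Week 12, and the laboratory and vital-sign tables could include samples up to about 16 weeks early; alternatively, the records could be pooled into Week 30.

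The size is illustrative: about 0.3 to 4.5 points on Week 28 ADA incidence, for 3% to 15% of values affected and a 10 to 30 point difference in ADA rate. The upper figure combines both upper assumptions; at 3% to 5% and a 10-point gap the shift is 0.3 to 0.5 points. The direction cannot be determined from the documents. The primary PK test, its alpha and its power are unaffected. The case for correcting it rests on the named secondary endpoint and on a labelling error that the plan itself acknowledges, not on a large expected effect.

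**What to change.** State one rule for all non-PK, non-efficacy early-termination records stored as Visit 15:

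- Identify them by actual assessment date.
- Exclude them from the Week 28 summaries and from the change from Week 12 to Week 28.
- Show them in a separate early-termination row, added to Appendix 1 and kept apart from Week 30, so that early leavers' ADA results are still reported.
- State in 19.5 which samples count as Week 28 for ADA, NAb and titre, with a window around the target day.
- Reword 7.3 so that it points to this rule and names the 7.4 handling of PASI and sPGA as the exception. Leave the PK sample rules in 6.6 and 20.1 as they are.

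A separate row is preferable to moving these samples to the nearest scheduled visit: under a 3-day window many early ADA results could become unscheduled and disappear from the summaries.

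The cost is SAP wording, one added output row and a few programming lines. Week 28 denominators become somewhat smaller: 165 × 0.03 ≈ 5 fewer per arm at the low assumption and 165 × 0.15 ≈ 25 fewer at the ceiling. Sample size, power and alpha do not change.

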#### 7.5. Statistical Tests

Confidence intervals will be 90% and all tests will be two-sided, unless otherwise specified in the description of the analyses.

#### 7.6. Common Calculations

For quantitative measurements, change and percent change from baseline at Visit X will be calculated as:

- Change from baseline at Visit X = Test Value at Visit X Baseline Value
- Percent change from baseline at Visit X = (Test Value at Visit X Baseline Value) / Baseline Value × 100

#### 7.7. Software Version

All analyses will be conducted using SAS Enterprise Guide version 8.2.

### 8. STATISTICAL CONSIDERATIONS

The following descriptive statistics will be presented in summary tables for non-PK data:

For continuous variables: the number of contributing observations (n), mean, standard deviation (SD), median, minimum, and maximum.

For categorical variables: the number and percentage of patients in each category.

If the original data has N decimal places, then the summary statistics will have the following decimal places:

Minimum and maximum: N;

Mean, median, lower and upper bounds of two-sided CI: N + 1;

Percentage of patients in each category, SD: N + 2

p-values will be presented with 4 decimal places

See Section 20 for descriptive statistics of PK data.

#### 8.1. Multicenter Studies

This study will be conducted by multiple investigators at approximately 36 study centers located in Europe. Randomization to treatment groups will be stratified based on Week 12/Visit7 PASI response: ≥ PASI50 to < PASI75 or ≥ PASI75.

Center pooling will not be carried out for use in analyses for this study.

Document: \\ieedc-vnasc01\Biosdata\\Viatris\HULIO\HAB34991\Biostatistics\Documentation\SAP

Author: Version Number: 2.0

Version Date: 29Nov2023

Template No.: CS\_TP\_BS016 Revision 7 Reference: CS\_WI\_BS005

Effective Date: 01Nov2021

Page 23 of 48

## 8.2. Missing Data

Safety, missing PK, or immunogenicity data will not be imputed.

Missing PASI and sPGA data will be imputed as per section 17.2.2.

#### **8.3.Intercurrent Events**

Not applicable.

## 8.4. Multiple Comparisons/ Multiplicity

Not applicable.

### 8.5. Examination of Subgroups

No subgroup analyses will be performed for this study.

## 9. OUTPUT PRESENTATIONS

Appendix 1 shows conventions for presentation of data in outputs.

The templates provided with this SAP describe the presentations for this study and therefore the format and content of the summary tables, figures, and listings to be provided by IQVIA Biostatistics.

### 10. DISPOSITION AND WITHDRAWALS

All patients who provide informed consent will be accounted for in this study.

## 10.1. Disposition

A clear accounting of the disposition of all patients who enter the study will be provided for the ENR, from enrolment to study completion. The patient disposition summaries include the following:

A summary of the number of screened patients, the number and percentage of screen failures and reasons for screen failure (Withdrawal by patient, Adverse Event, lost to follow up, Entry criteria not met, Sponsor decision, and Other), using the SCR population.

Document: \\ieedc-vnasc01\Biosdata\Viatris\HULIO\HAB34991\Biostatistics\Documentation\SAP

Author: Version Number: 2.0

Version Date: 29Nov2023

Template No.: CS\_TP\_BS016 Revision 7 Reference: CS\_WI\_BS005

remplate No.: OC\_11\_BOO10 Nevision /

Page 24 of 48

Patients entering the Run-in Period at Week 1, patients completed Run-in period, patients discontinued during the run-in period, reasons for not completing the Run-in Period, patients Run-in failed, patients completed the Run-in Period but not randomized, reasons for completed Run-in period but not randomized, patients randomized at Week 12, patients completed the full course of study treatment, patients discontinued treatment, reason for treatment discontinuation, patients completed the study, patients discontinued the study, reason for study discontinuation will be summarized by planned treatment group.

Additionally, separate tables for reasons for exclusion from each analysis population, including inclusion and exclusion criteria will be presented for the Enrolled population.

#### 10.2. Protocol Deviations

Protocol deviations are the deviations from the procedure outlined in the protocol. All the Protocol Deviations (PDs) will be summarized using the Run-in period population as obtained from Clinical Trial Management System (CTMS) logs. PDs will be identified and discussed with the Investigator/Sponsor in PD review discussion to categorize them, and to finalize analysis population assignment.

Any PDs will be categorized into critical, major, and minor protocol deviations and will be summarized based on severity categories. An additional table summarizing the number and percentage of patients with Important PDs will be presented. Critical and Major protocol deviations having impact on primary analysis will be considered while finalizing the Per Protocol (PP) population. PDs log will be used for reporting purpose in tables.

